Differences between Conventional In-Centre and Home Hemodialysis

Although ease of cannulation is important in-centre, it is even more important for patients at home. It is unclear if the potential ease of use of buttonhole cannulation might lead to enhanced home hemodialysis recruitment rates and reduced training time. The ease of use of CVCs likely contributed to the decreased training time that was required for patients with this type of access in the Frequent Hemodialysis Network Trial. There is emerging controversy about reduced pain on needle insertion with buttonhole cannulation in centre. However, it is unclear if using the buttonholes more frequently might result in reduced cannulation pain secondary to 'enhanced' maintenance of the fibrous tract. Lastly, for patients who are treated in-centre, needles are typically inserted by skilled allied health team members. At home, needles are inserted by the patient or a family member helper who must be trained to perform home hemodialysis. It is unclear if allied health team members are more likely to follow strict rules for cleanliness compared to patients at home such that infection risks might be less in-centre. Also, the enhanced frequency of use of the buttonholes for high dose hemodialysis might be associated with an increased risk of infection.

Summary and Conclusions

There is increasing interest in high dose home hemodialysis therapies. Although both needle cannulation techniques have been used for home hemodialysis, the relative benefits and risks of the two techniques have never been explored in a randomized controlled trial. The potential advantages of buttonhole cannulation for this patient population may be enhanced recruitment, reduced training time, reduced aneurysm formation and a reduced number of interventions. The reduction in training time may result in significant savings to the hospitals in which reimbursed training days are fixed. The benefits may be offset by the potential for an increased risk of infection. However, the potential benefits and risks of buttonhole cannulation versus step-ladder cannulation remain speculative as they have not been studied in a rigorous prospective trial of home hemodialysis patients treated with high dose hemodialysis.

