All eligible patients will be randomized to either step ladder or buttonhole cannulation technique for needle insertion. Randomization will be determined via a computer generated randomization code with stratification by site and AVF type (incident vs. prevalent). The group assignment will be kept in sealed opaque envelopes and provided to sites via the coordinating centre at the time of study consent. Only the investigators will be aware of the training time as an objective of the study as the intervention cannot be blinded and the outcome is potentially influenced by factors other than needle insertion technique. For consent and the remainder of the health team; the purpose of the study will be to determine feasibility, infection rates and other complications associated with the two different needle insertion techniques. Each Research Ethics Board will need to approve that one of the study objectives will be concealed.

Data collection forms will be developed with the assistance of the Ottawa Hospital Methods Centre and pilot tested at 2 sites (Ottawa and University Health Network) prior to the creation of an electronic data capture form to be used by all participating sites. The amount of time required to consent patients, complete the case report forms and follow each patient for the complication outcomes will be documented at these two sites so that this data can be used to inform the definitive trial budget.

After ensuring that the case report forms and access documentation tool are useable and all necessary information is being collected, the remaining programs will begin to recruit patients. Each program will be responsible for keeping a log of all patients who are training for home hemodialysis and the proportion of patients who are candidates for the study. Of the patients that are candidates for the study, the number of patients who are randomized to the study will be tracked. Reasons for not participating in the study for all potential candidates will be documented and reviewed at quarterly meetings. If themes are identified that are limiting enrollment, solutions will be proposed by the investigators and implemented if possible.

Needle Insertion Techniques

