Step ladder insertion technique: The AVF site will be cleaned with 2% chlorhexidine/alcohol 70% prior to needle insertion. If the patient develops contact dermatitis, the AVF site will be cleansed with 2% cholorhexidine, 70% alcohol, povidone iodine or antibacterial soap alone. Sites will be rotated with needles placed at least 2-3cms between needle tips.

Buttonhole insertion technique: The AVF site will be cleaned as above except cleansing will occur before and after buttonhole scab removal. A minimum of 2 buttonholes will be developed for patients undergoing double needle hemodialysis (1 for single needle) by a nurse or patient (at the discretion of the health care team) trained in the technique.

Buttonhole sites will be created at a 20-30 degree angle at least 3 cm from the arterial or venous anastomosis. Once the buttonhole is established with sharp needles, blunt needles will be used. At this time, the patient will be instructed on needle insertion technique if they were not taught to develop the buttonholes initially. Scabs will be removed from the buttonholes either with an alcohol or saline soaked gauze; the use of needles or tweezers to remove scabs will be discouraged.. Post hemodialysis, mupirocin (or other suitable antimicrobial cream if patient develops contact dermatitis/allergy, for example: polysporin, betadine ointment or PHMB antimicrobial dressings) will be applied to the buttonhole sites to reduce the risk of infection.

Time to Train

Patients will be trained according to usual home dialysis unit policies with the exception of the needle insertion protocol. Any difficulties with training needle insertion will be documented by the nurse educator. The time required to teach proficiency in self cannulation will be documented (the number of days required for the patient to competently place their own needles without the assistance of the dialysis nurse). Total training time will be the numbers of days required from start of training to discharge to home. Any missed days secondary to statutory holidays, appointments or other illness unrelated to access needle insertion technique will not be included in the training days calculation. If a patient has to return to the home dialysis unit to develop a new buttonhole site, the training time will also be documented and added to the total training time.

AVF Access Complications

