Any additional days of training and any days required for re-training will be included in the overall cost. Any differences in the cost of the blunt versus sharp needles and the mupirocin for buttonhole cannulation will be included in the overall cost. Treatment for infection including antibiotics and hospitalizations will be included and costed according to established principles. Similarly, the cost associated with any required angiogram (leading to an angioplasty), angioplasty or surgical revision will be included.

Visual Analogue Scale – Pain with Needling (Appendix 1)

All patients will continue (or start) with the step ladder insertion technique for the first 2 to 3 days at which time they will use the validated 10 cm visual analogue scale to rate the pain they experience with needle insertion. The visual analogue scale will be repeated at 2 additional time points – at the end of training and approximately 2 months after graduating home hemodialysis training. As many of the programs train 3 days per week, the additional time point is to capture the potential differences in perceived needling pain with increased frequency of needle insertion. It is unclear if buttonholes are easier to maintain when used more than 3 days per week as this may be associated with less pain on needle insertion. Topical anesthetics will not be withheld during assessments of pain with the visual analogue scale but the requirement for use will be documented.

Sample Size Calculation

There are a limited number of patients who start home HD each year in Canada. If we are unable to get at least 70% enrollment in the pilot study – it is very unlikely that we will be able to successfully undertake a study with a larger sample size. For the purposes of the feasibility pilot, the first 2 centres (Ottawa and University Health Network) will recruit participants for 18 months with the remaining centre's participating for 12 months. All patients who are eligible for the study will be approached for recruitment. Our goal is to demonstrate that we can successfully recruit. For the definitive study to explore the differences in training time between the two needle cannulation techniques: The mean number of training days for patients with an AVF in the FHN studies was 27.7 with a standard deviation of 10.4 (20). This was reduced by 5 days for patients using a central venous catheter. Assuming that a buttonhole cannulation would

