have a similar impact on training time, 69 patients per groups would give us 80% power to detect this difference. The number required in the trial increases to 107 if the difference is 4 days.

Analysis

For the purposes of the pilot study, basic demographic characteristics of the included and excluded patients will be described using appropriate descriptive statistics. This data will be retrospectively collected on patients who were not enrolled in the study. The percent of qualified patients enrolled in the study for the pilot study to be successful will be $\geq 70\%$. The secondary outcomes will be analyzed on an intent to treat basis upon completion of the main study assuming that this trial is feasible. The comparison of mean training times will be done with an un-paired t-test. A linear regression analysis will also be undertaken to examine predictors of training time including age, sex and Charlson comorbidity score in addition to needle insertion technique. Any differences in pain scores depending of frequency of cannulation will be explored within cannulation techniques. If no differences exist by frequency of cannulation, the data will be combined and the median pain scores will be assessed with a Wilcoxon rank sum test. The different types of complications and costs will be categorized and the overall mean differences will be assessed with an unpaired t-test. Any differences in outcomes by frequency of cannulation will also be explored within each of the secondary outcomes.

For patients who return to train on cannulation technique (started home HD with a CVC or other access that failed); their data will not be included in overall training time but all other study outcomes will be tracked and included in the analysis infections and complications.

The retrospectively collected demographic data will be analyzed in order to describe the patient population.

Data Safety Monitoring Board

Drs. [name] and [name] in addition to [name] (vascular access coordinator) have agreed to monitor the outcomes of this study. If we detect infection rates that are comparable to or greater to the benchmark for central venous catheters as adopted by the Ottawa Hospital - the study will be stopped (external benchmark bacteremia rate of 4.6 per 100 patient months, Nephrology News and Issues 2005, 37-43)

Study Investigators

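### Training time is compared with a t-test that ignores the randomisation strata, and the planned regression names neither site nor AVF type, so precision may be lost

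*Combined protocol and SAP*

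**What the plan says.** On allocation, the Study Overview states: "Randomization will be determined via a computer generated randomization code with stratification by site and AVF type (incident vs. prevalent". It gives no block size.

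On the comparison of training time, the Analysis section states: "The comparison of mean training times will be done with an un-paired t-test". It then adds a linear regression to examine "predictors of training time including age, sex and Charlson comorbidity score in addition to needle insertion technique". That list is open, so site and AVF type are not excluded, but neither is named. No section provides for a stratified or stratum-adjusted analysis.

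On how training is run, the Time to Train section states: "Patients will be trained according to usual home dialysis unit policies with the exception of the needle insertion protocol".

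Training time is a secondary outcome, to be analysed after the main study if the trial proves feasible. It is also the outcome that sizes the definitive trial. The Sample Size Calculation section takes an SD of 10.4 days and a 5-day difference and arrives at 69 per group for 80% power, or 107 if the difference is 4 days.

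**The concern.** Stratifying by a factor pays off in precision only if the analysis uses that factor. When strata predict the outcome and allocation is balanced within them, the true sampling error of the treatment difference shrinks. An ordinary t-test still computes its standard error from the total variance. The result is an interval wider than it need be and a test that rejects too rarely under the null.

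The plan already intends a regression with technique in it, so the remaining gap is that the stratification factors are not pre-specified as terms. An open predictor list also leaves the model to be settled later, in a trial where the intervention cannot be blinded.

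The stakes are modest. No pilot decision rests on training time. But the protocol stresses that few patients start home hemodialysis in Canada each year, and any precision gained from factors recorded at randomisation needs no extra patients.

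**Working it through.** **Inputs from the documents.** SD 10.4 days; difference 5 days (4 as the alternative); 69 per group (107); 80% power; strata are site and AVF type (two levels).

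**Assumptions.**
- Two-sided 5% test and 1:1 allocation (neither is stated).
- 10.4 is the total SD, including any variation between strata.
- Four sites, one per city listed under Study Investigators, with additive site and AVF effects.
- R², the share of training-time variance explained by the strata, is 0, 0.1, 0.2 or 0.3. The documents give no value. These correspond to a between-stratum SD of √R² × 10.4 = 0, 3.3, 4.7 and 5.7 days.

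**Step 1: reproduce the stated sizes.** n = 2 × (1.960 + 0.842)² × 10.4² / 5² = 67.9, so 68 per group; the noncentral t gives 69. For 4 days the same formula gives 106.1, so 107; the noncentral t gives 108. A one-sided 5% test would give 54 and 84. The stated figures therefore reproduce, and they rest on the unadjusted SD.

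**Step 2: the t-test's precision.** SE = 10.4 × √(2/69) = 1.77 days. The 95% CI half-width is 1.978 × 1.77 = 3.50 days, whatever the value of R².

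**Step 3: site and AVF type in the model.** Residual SD = 10.4 × √(1 − R²). The strata use 3 + 1 = 4 degrees of freedom, leaving 138 − 2 − 4 = 132.

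| Assumed R² | 0 | 0.1 | 0.2 | 0.3 |
|---|---|---|---|---|
| Residual SD (days) | 10.40 | 9.87 | 9.30 | 8.70 |
| CI half-width (days) | 3.50 | 3.32 | 3.13 | 2.93 |
| Power at 69 per group, 5 days | 80.0% | 84.0% | 88.0% | 91.8% |
| n per group for 80% power, 5 days | 69 | 63 | 56 | 49 |
| n per group for 80% power, 4 days | 108 | 97 | 86 | 76 |

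**Step 4: the t-test under perfect balance within strata (normal approximation).** Type I error = 2Φ(−1.96/√(1 − R²)) = 5.0/3.9/2.8/1.9%. Power = Φ((5 − 1.96 × 1.77) / (1.77 × √(1 − R²))) = 81/82/83/85%.

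**Step 5: simulation.** 138 patients, 12,000 runs per cell; four sites assumed to hold 35/30/20/15% of patients, ten sites assumed equal, AVF types 50/50. The adjusted model here has site and AVF type only.

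| Setting | Result | R² = 0 | 0.1 | 0.2 | 0.3 |
|---|---|---|---|---|---|
| 4 sites, blocks of 4 | t-test type I error | 4.7% | 3.9% | 2.9% | 2.0% |
| | Power, t-test | 80.4% | 81.6% | 82.0% | 84.3% |
| | Power, adjusted | 80.4% | 84.3% | 87.8% | 91.8% |
| 4 sites, no balance | Power, t-test | 79.7% | 79.4% | 80.0% | 80.0% |
| | Power, adjusted | 78.4% | 82.5% | 87.0% | 90.9% |
| 10 sites, no balance | Power, t-test | 79.1% | 80.1% | 79.7% | 79.2% |
| | Power, adjusted | 76.3% | 81.3% | 85.2% | 89.1% |

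With four blocked sites the adjusted analysis kept its type I error at 4.7–5.1%. Without balance (four sites) the t-test's type I error is about 5%, so it is then neither conservative nor inflated.

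**Step 6: the full proposed model.** If age, sex and Charlson score are added and carry no information, the total cost at R² = 0 is about 0–1 power point with four blocked sites. With ten sites and no balance it is about 3–4 points, and there is little or no gain at R² = 0.1.

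**The case against.** The strongest reply is that nothing here is an error. The t-test is valid, its stated power is correct, and the regression list is open enough to take site and AVF type. All of that stands, which is why this is an improvement and not a defect.

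The second reply is that every gain depends on an R² that the documents do not give. That also stands. At R² = 0 nothing is lost, so the most that can be said is that precision may be lost.

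The third is that the textual support for stratum effects is thin. A reader might draw on four other statements, but none establishes a difference between strata in training days:
- "savings to the hospitals in which reimbursed training days are fixed" concerns reimbursement, not the number of days a unit needs.
- "As many of the programs train 3 days per week" describes a weekly schedule and is there to justify a pain assessment; if training days are counted as sessions, it need not change the total.
- "by a nurse or patient (at the discretion of the health care team) trained in the technique" applies to the buttonhole arm only. It would make the effect vary by site, which an additive site term does not capture.
- "All patients will continue (or start) with the step ladder insertion technique for the first 2 to 3 days" is not tied to AVF type.

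Only the statement that training follows each unit's own policies firmly supports a site effect, and it carries no number.

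The fourth is that adjustment is not free. With many small sites and no balance within strata it can cost a few points, and neither the block size nor the definitive number of sites is stated. This is a fair limit on the recommendation. It is an extreme case, however, since the plan does stratify.

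**Conclusion.** The point holds as a modest, conditional one. The plan stratifies by two factors, then compares training time without them and does not name them in its regression. If those factors predict training days, the t-test may forgo precision. With four blocked sites, the difference in power is nil at R² = 0 and about 3, 6 and 8 points at R² = 0.1, 0.2 and 0.3. Those R² values are assumptions, so the actual size is unknown.

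Three stronger readings are not supported. A reader might infer that the t-test is biased or its type I error inflated; it is unbiased, and its error rate is nominal or lower. A reader might infer that 69 per group is too few; it is the right size for the planned test. A reader might extend the point to complications, which are also compared by t-test without a term for time at risk; the 12-month eligibility criteria point to similar follow-up, and nothing shows that it differs by arm.

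**What to change.** In the Analysis section, make the already planned linear regression the main comparison of training time. Specify technique, site and AVF type as additive terms, plus age, sex and Charlson score. Report the adjusted difference in days with its 95% CI, and keep the un-paired t-test as a supporting analysis. Additive terms are preferable to site-by-AVF cells, which would be small.

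The change is one of wording. Site and AVF type are known at randomisation, and the other covariates are already collected. With four sites the strata use 4 degrees of freedom (10 with ten sites). The cost in power if the strata do not matter is that given in Step 6. Stating the block size would show which of the simulated settings applies. If the definitive trial will have many small sites, the way they enter the model should be fixed before the data are seen.

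### The planned look at cannulation frequency and pain relies mainly on the 2-month score within each technique, so a frequency effect cannot be told apart from change over time

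*Combined protocol and SAP*

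**What the plan says.** The section Visual Analogue Scale – Pain with Needling has a first rating in the opening days, when every patient uses step ladder: "All patients will continue (or start) with the step ladder insertion technique for the first 2 to 3 days". Two later ratings are set: "The visual analogue scale will be repeated at 2 additional time points – at the end of training and approximately 2 months after graduating home hemodialysis". The last rating is justified by the three-day training week that many, though not all, programs use, and its purpose is given directly: "the additional time point is to capture the potential differences in perceived needling pain with increased frequency of needle insertion". The clinical question behind this purpose is also put in words: "It is unclear if buttonholes are easier to maintain when used more than 3 days per week". The section's thought is that more frequent use may go with less pain.

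The Analysis section then states: "Any differences in pain scores depending of frequency of cannulation will be explored within cannulation techniques". The result acts as a gate on the between-arm rank-sum test: "If no differences exist by frequency of cannulation, the data will be combined and the median pain scores will be assessed with a Wilcoxon rank". A later sentence extends the exploration by frequency to the other secondary outcomes.

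Technique is randomized, stratified by site and AVF type; frequency is not. For pain, the plan gives no time term, no arm-by-time comparison, no constant-frequency comparator, no definition of frequency and no statement of which visits are compared.

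**The concern.** The background sections treat frequent use as a reason why in-centre pain results may not carry over to home, and pain is a secondary objective. The extra rating is there to inform that question.

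A patient who trains 3 days per week and then dialyses more often at home has both a higher frequency and a later date at the second of the two follow-up ratings. Within one arm, the comparison cannot separate the two. The protocol itself contains other reasons for pain to change over that interval:

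- Patients are learning to place their own needles.
- Buttonholes start with sharp needles and move to blunt ones once established.
- Topical anesthetic use may vary. The plan says "Topical anesthetics will not be withheld during assessments of pain with the visual analogue scale but the requirement for use will be documented", but no adjustment is planned.

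Two things are at stake. Ordinary change over time could be reported as an effect of needling frequency. It could also count as a difference by frequency, in which case the condition for the combined between-arm pain test is not met and the plan names no alternative.

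**Working it through.** **The plan's own figure.** The only sample size is for training time: SD 10.4 days, difference 5 days, 80% power. Alpha is not stated; two-sided 0.05 is assumed. The formula n = 2(1.96 + 0.842)² × 10.4² / 5² gives 67.9, so 68 per group; the exact t-test gives 68.9, so 69, as stated. For 4 days the same formula gives 106.1, so 107, as stated. These figures are not in question. None is given for pain; 69 per arm is used below only as the size of the definitive study, on whose completion the secondary outcomes are to be analysed.

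**Assumed inputs (not in the documents).** VAS SD 2 cm; correlation r between the two later ratings 0.5 to 0.7; a fall d in pain over time of 0.3, 0.5 or 1.0 cm; true frequency effect zero.

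**Within-arm paired test, closed form.** SD of change = 2 × √(2(1 − r)), which is 2.00 cm at r = 0.5 and 1.55 cm at r = 0.7. Noncentrality = d × √69 / SD of change. For d = 0.5:

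- r = 0.5: 0.5 × 8.307 / 2.00 = 2.08, so p < 0.05 in 53% of trials.
- r = 0.7: 0.5 × 8.307 / 1.55 = 2.68, so p < 0.05 in 75% of trials.

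**Simulation.** Mean 3 cm, scores limited to 0–10, paired Wilcoxon test within the buttonhole arm, t-test for change between arms, 69 per arm. Limiting the scores lowers the rates a little; repeat runs differ by a few percentage points.

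| Fall over time | Within-arm test, no frequency effect | Change between arms, fall common to both | Change between arms, fall in buttonhole arm only |
|---|---|---|---|
| 0.3 cm | 23–34% | 4–6% | 13–21% |
| 0.5 cm | 48–70% | 4–6% | 31–45% |
| 1.0 cm | 97–100% | 4–6% | 82–95% |

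With no fall, the within-arm test is significant in about 5% of trials. At an assumed 25 per arm it is significant in about 9–13%, 21–31% and 63–84% for the three falls. With SD 2.5 cm, r = 0.5 and 69 per arm, a paired t-test gives 37% for 0.5 cm and 90% for 1.0 cm.

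**What the last column means.** Comparing change between arms removes only drift that both arms share. Tract formation and the move to blunt needles occur only with buttonholes. They would appear as a difference in change between techniques with no frequency effect present. Conversely, a frequency benefit equal in both arms would not show there. That comparison tests technique by time, not frequency.

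**Comparing patients whose frequency rose with those whose did not.** With an assumed 70/30 split and equal drift in both groups, the false-signal rate is 4–6%. If drift differs between the groups by 0.5 or 1.0 cm, it is about 15–22% or 44–63% in the buttonhole arm at 69 per arm.

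**The case against.** The strongest reply is that the Analysis section names no test, no pair of visits and no definition of frequency. It only says that differences will be explored. Because the same exploration is planned for training time, costs and complications, which have no end-of-training versus 2-month contrast, frequency could be meant as a characteristic of the patient. Only many, not all, programs train 3 days per week, so patients on different schedules could be compared at the same visit without equating frequency with time.

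This stands in part. A reader might infer that the plan tests whether pain changed between the two visits and that any change will be called a frequency effect. The documents do not say so. They do say that the 2-month rating exists to capture increased frequency, which makes the visit contrast the natural reading for pain. The between-patient reading is nowhere defined either. It would be non-randomized and tied to program, because training frequency is described as a program feature.

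It is also fair that this is an exploratory look at a secondary outcome, in a trial whose primary outcome is feasibility. The missing pooling criterion is a separate weakness of the gate; the point here is that change over time can feed into it.

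**Conclusion.** The concern holds in a limited form. For patients whose frequency rises on going home, the contrast that the two sections point to confounds frequency with time since training, and its result can decide whether the combined between-arm pain test is run. With no frequency effect, an assumed 0.5 cm fall gives a significant within-arm result in roughly 48–70% of trials at 69 per arm, against a nominal 5%. That range rests on the assumed SD, mean, correlation and fall, on a paired test the plan does not specify, and on treating the visit contrast as the frequency contrast.

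Two further readings are tempting and unsupported. One is that the randomized comparison of pain is itself biased: at a single visit, a trend common to both arms does not bias it. The other is that comparing change between arms would isolate frequency: it does not, because buttonhole-specific maturation also enters it.

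The wording should be settled before the secondary outcomes are analysed.

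**What to change.** Replace the sentences on pain and frequency in the Analysis section with text to this effect:

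- Pain will be compared between the randomized arms, by intention to treat, at the end of training and at 2 months. These comparisons will not depend on a prior finding about frequency.
- Change in pain between those visits will be compared between arms and reported as a technique difference in change, not as an effect of frequency.
- Change within an arm will be reported as change over time only.
- Sessions per week will be recorded at each pain rating. Any comparison of patients whose frequency did and did not rise will be exploratory, adjusted for site and technique, and labelled non-randomized.
- If nearly all patients' frequency rises, the report will state that frequency and time cannot be separated.

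Visits and treatment are unchanged. The cost is analysis wording and one added data item, since no section specifies recording frequency at each rating. The frequency question will have low power. For an assumed 1 cm frequency effect in buttonhole patients only, with no time trend, r = 0.6, 69 per arm and a 70/30 split, the comparison by whether frequency rose has about 52% power. The confounded within-arm test has 84%.

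### The only between-arm pain test is conditional on an exploratory look at cannulation frequency that has no criterion, no alternative analysis and no stated time point or unit

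*Combined protocol and SAP*

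**What the plan says.** The pain scale is completed three times (Visual Analogue Scale section). The first score is taken in the opening 2 to 3 days, while every patient is needled by step-ladder. After that, "The visual analogue scale will be repeated at 2 additional time points": the end of training and about 2 months after graduation. Many programs train 3 days per week, and the section explains that "the additional time point is to capture the potential differences in perceived needling pain with increased frequency of needle insertion".

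The Analysis section handles pain in two steps. First, "Any differences in pain scores depending of frequency of cannulation will be explored within cannulation techniques". The second step is a rank-sum test under a condition: "If no differences exist by frequency of cannulation, the data will be combined and the median pain scores will be assessed with a Wilcoxon". A later sentence adds that "Any differences in outcomes by frequency of cannulation will also be explored within each of the secondary outcomes".

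On timing and population, "The secondary outcomes will be analyzed on an intent to treat basis upon completion of the main study", provided the trial proves feasible. For patients who return to train on cannulation, "their data will not be included in overall training time but all other study outcomes will be tracked".

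**The concern.** Objective 4 poses one question between techniques, and the plan has one between-arm test to answer it. That test is written only for the case where the frequency look finds nothing. Four things are missing:

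- a test, threshold or set of frequency categories that defines no difference;
- a between-arm analysis for the case where a difference is found;
- the visit, or visits, at which the arms are compared;
- whether the combined data are pooled over groups of patients or over visits of the same patient.

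The unwritten branch is not remote, since the 2-month score was added because pain might change with frequency. The condition is also not needed to study frequency, which the later sentence already explores for every secondary outcome. At stake are the error rate and the interpretability of the pain result: two analysts could follow this text and run different tests, having seen the data.

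**Working it through.** **The plan's own figures.** The documents give no sample size, SD or effect for pain. The stated sizes concern training time (SD 10.4 days, difference 5 or 4 days). With two-sided 5% (assumed) and 80% power, n = 2 × (1.960 + 0.842)² × 10.4² / d². This gives 67.9 for d = 5 and 106.1 for d = 4; the t-based solutions are 68.9 and 107.1. The stated 69 and 107 reproduce. Below, 69 per arm serves only as an example size.

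**Assumptions.** Normal scores, no true technique difference, a 5% look within each technique, and an equal frequency split where patients are split. None of these is in the documents.

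**Step 1: how often the look blocks pooling.**
- No frequency effect: 1 − (1 − 0.05)² = 0.0975. With 10% looks, 1 − 0.90² = 0.19.
- Real effect of 0.4 SD between two halves of an arm of 69: power per look is 0.383, so blocking occurs in 1 − (1 − 0.383)² = 0.62 of trials.

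**Step 2: if frequency differs between patients and each frequency group is then tested at 5%** (this branch is assumed).
- At least one false positive, by simulation: 0.079 with no frequency effect, 0.091 with 0.2 SD, 0.101 with 0.4 SD.
- The excess arises because the look and the group contrasts share data. The pooled test is independent of the look, so it contributes 0.9025 × 0.05 = 0.045. The remaining 0.034 comes from the 9.75% of blocked trials, so about 35% of those (0.034 / 0.0975) show a false positive.
- Power: a difference that the pooled test detects with 80% power has noncentrality 2.802. In a group holding share f of the patients, power is Φ(2.802 × √f − 1.96): 0.51 for f = 0.5, and 0.65 and 0.34 for a 70:30 split. Confidence intervals widen by 1/√f: 1.41, or 1.20 and 1.83.

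**Step 3: if frequency means visit.** Every patient contributes at both visits, so the power and interval losses of step 2 vanish. The false positives do not. Take the rule as testing the mean of the two later visits if the look is clear, and each visit at 5% otherwise. For within-patient correlation 0.3 to 0.7, simulation gives at least one false positive in about 6–7% of trials with no visit effect and 8–10% with a 0.4 SD visit effect.

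**Step 4: if combining means entering both later scores of each patient as independent observations.** With within-patient correlation r, the true variance of the mean difference is (1 + r) times the assumed one, so the type I error is 2 × [1 − Φ(1.96/√(1 + r))]:

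| r | Type I error |
|---|---|
| 0.3 | 0.086 |
| 0.5 | 0.110 |
| 0.7 | 0.133 |

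Rank-sum simulations at 69 per arm gave 0.080, 0.106 and 0.122. One score per patient stays near 0.05.

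**Step 5: the first score.** Linear adjustment for it cuts the variance by r²: 9% at r = 0.3 and 25% at r = 0.5, which narrows the interval by 5% and 13% (width factor √(1 − r²) = 0.954 and 0.866).

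**The case against.** The strongest reply is that the size is built on readings the plan does not state. No section defines frequency groups of patients, and the Visual Analogue Scale section ties frequency at least partly to visit. Separate tests by frequency are written nowhere; the later sentence on exploring outcomes by frequency may be the intended fallback. Pain is the fourth of five secondary objectives, the definitive trial is sized on training time, and the analysis waits for a main study that may not take place.

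Much of this stands. A reader might infer that the plan halves the power for pain, or that it prescribes split tests. The documents support neither: the fall from 80% to 51% needs both a between-patient split and the assumed branch. A reader might also infer that pain goes uncompared once a frequency difference appears. The plan is silent there, and a comparison by frequency group is the likelier intent. Nor does leaving the first score unused bias the comparison; it only costs precision.

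What does not stand is that the later sentence fills the gap. It specifies no comparison between techniques. Nor does reading frequency as visit remove the problem, as steps 3 and 4 show.

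**Conclusion.** The concern holds as a data-dependent analysis rule with an undefined trigger and no second branch. That conclusion rests on the text alone. Its size is illustrative: pooling blocked in 9.75% of trials with no frequency effect; at least one false positive in about 8–10% of trials (between-patient reading) or 6–10% (visit reading), against 5%; and about 9–13% if two visits per patient are treated as independent. These figures assume 5% looks, normal scores, 69 per arm, within-patient correlations of 0.3 to 0.7 where visits are involved and, for the false-positive ranges, separate tests after a positive look.

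It should be corrected, but reach is limited. A reader might infer that the vanguard trial's own result is in doubt; it is not, because the 70% enrolment criterion does not use pain scores. The point matters for the definitive trial, for which pilot data are kept only if the protocol is unchanged, feasibility is established and the sample size is achievable.

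**What to change.** Amend the Analysis section before outcomes are compared by arm:

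- Compare the arms on pain unconditionally, with one score per patient at each visit.
- Name either the end of training or 2 months as the main time point, and report the other as supportive.
- Keep the rank sum test, and add a Hodges-Lehmann difference with 95% confidence interval so that the result is in scale units.
- Keep cannulation frequency as an exploratory technique-by-frequency analysis that does not decide whether or how the arms are compared.
- As a supporting precision analysis, adjust for the first score by linear ANCOVA. State the caveat that this score is self-reported after unblinded allocation, since assignment is provided at consent, although both arms are then needled by step-ladder.

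The cost is wording only. All the scores are already collected, and no visit, procedure or sample size changes.
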